3.2.1.1.2 Qualitative exposure

A vital goal of the questionnaire is to obtain general exposure information and to determine if a relationship exists between such exposure and potential health issues. “Exposure” refers to “total exposure,” and thus includes both exposure related to residential and occupational sources (e.g. where you have lived and worked and for how long, nature of the job), as well as other secondary sources, such as diet and lifestyle (e.g. water sources, hobbies). Accordingly, detailed questions are included that encompass these areas to gauge both current and past individual exposure.

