3.4 Study Limitations

Many factors can influence health and confound the measures of health including: age, gender, family history, as well as social, physical and economic environment. These have been taken into account in the CHAP project wherever possible. There has been the addition of the three confounding metals, lead, mercury and cadmium. We will be able to determine the levels of CoCs in the body but where there is the presence of multiple chemicals, it may be difficult to deduce any association with one particular contaminant. In evaluating the exposure and levels of CoCs in the body, it should be noted that the exposure does not indicate the level of lifetime exposure or the highest exposure that an individual has had. The level of CoCs detected in the body measure the level of metal at that moment of time. The measures will not be able to differentiate between recent exposure or levels of metal from a previous or historical exposure, in addition the measures will not be a reflection of the highest exposure or the duration of the exposure. The tests for CoCs will only measure the presence of CoCs and not the end organ effect of the CoCs.

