6.2.1.2 Exposure

The exposure information collected falls into five categories: residential, occupational, lifestyle/dietary, educational, and other exposure. The residential information will include address, period of stay, type of dwelling, and age of residence. From this, information on the number of years of residency in Port Colborne can be calculated. There is a child specific section that collects information on children who have had more than one permanent address. Residential information will also be used to assign exposure to CoCs

into two categories. Specifically, exposed which equates to the Rodney Street area versus non-exposed which equates to all other geographical locations within Port Colborne. Occupational exposure is assessed for specific high exposure industries. Details are collected for job description, activity, and duration of employment. Lifestyle/dietary exposure includes information collected on the source of drinking water, gardening, high exposure non-occupational hobbies, smoking, second-hand smoke, and alcohol consumption. Education exposure is specific to children; the questionnaire is designed to collect information about schools attended and the duration of attendance. Other exposure information collected includes data on jewellery that pierces the skin.

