Univariate statistics will be calculated for each chemical, as determined by laboratory analysis, to summarize the levels of the CoCs. These statistics will include: the mean, median, range, standard deviation and upper and lower percentiles. Tests for normality will be conducted to determine whether transformations of the CoCs values may be necessary for some multivariate modeling procedures. Variations in exposure levels within Port Colborne will be explored by calculating these summary statistics separately across different areas within the city. Differences across regions will be evaluated using multivariate regression analyses. Lognormal transformations are frequently applied to exposure distributions that are skewed. For CoCs with a large number of non-detectable levels, logistic regression analysis will be used to model those with exposure above the median CoCs level, relative to those with exposure below the median value.

Logistic regression methods will be used to evaluate the relationship between exposure to CoCs and selected health conditions. Because exposure to CoCs has been measured using two instruments (i.e., biological specimens and health questionnaire items), logistic regression analysis will be performed using these two series of independent variables. Pearson correlations coefficients and categorical analyses will be used to examine the concordance between the exposure measures from the laboratory and the summary measure estimated from the questionnaire.

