Lifestyle and Dietary Information of Participants, by Sampling Areas,
CHAP Comprehensive Health Questionnaire, Fall 2002

	Area 3	Areas 1, 2, 4, 5	Total for Port Colborne	p-value [†]
	N (%)	N (%)	N (%)	
Occupation related to Exposure *				
Yes				
No				
Primary Source of Drinking Water				
Municipal				
Well				
Bottled				
Gardening Activity				
Yes				
No				
Non-occupational Activities related to Exposure to CoCs **				
Yes				
No				
Cigarette smoking status				
Never				
Current				
Former				
Unknown				
Exposure to second-hand Smoke				
Never				
As a child only				
As an adult only				
As a child and adult				
Current alcohol consumption				
Less than once a month				
1 To 3 times a month				
4 to 12 times a month				
> 12 times a month				
Jewelry piercings				
Yes				
No				

* Includes the following occupations: mining; metal cutting, grinding and refining; smelting; foundry work; steel making; welding; plumbing; brazing; plumbing; shipbuilding; metal plating or electroplating; boiler maker/repairer

** Includes painting, renovations, landscaping and automotive work

† p-value is based on Chi-square for comparison of proportions.

Table 5.
Prevalence of Selected Health Conditions of Participants, by Sampling Areas,
CHAP Comprehensive Health Questionnaire, Fall 2002

	Area 3	Areas 1, 2, 4, 5	Total for Port Colborne	p-value [†]
	N (%)	N (%)	N (%)	
Chronic Bronchitis				
Emphysema / Chronic Obstructive Pulmonary Disease				
Other Allergies				
Asthma				
Hypertension				
Heart Disease				
Thyroid Condition				
Stomach / Intestinal Ulcers				
Gastroenteritis				
Peripheral Neuropathy				
Arthritis				
Parkinson's				

[†] p-value is based on Chi-square for comparison of rates from Area 3 to Areas 1, 2, 4, and 5 after adjustment for differences in the age and sex distribution of the two populations.

Table 6.
External Comparison of Selected Health Conditions of Participants, by Sampling Areas,
CHAP Comprehensive Health Questionnaire, Fall 2002

	Port Colborne	Ontario	p-value [†]
	Prevalence	Prevalence	
Chronic Bronchitis			
Emphysema / Chronic Obstructive Pulmonary Disease			
Food Allergies			
Other Allergies			
Asthma			
Dermatitis			
High Blood Pressure			
Heart Disease			
Anaemia			
Thyroid Condition			
Stomach / Intestinal Ulcers			
Gastroenteritis			
Jaundice			
Parkinson's Disease			
Peripheral Neuropathy			
Parkinson's			

[†] p-value is based on Chi-square statistic of rates after direct standardization by age and sex. .

Table 7.

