 - ___ Trades certificate or diploma from a vocational school or apprenticeship training
 - ___ Non-university certificate or diploma from a community college, CEGEP, school of nursing, etc.
 - ___ University certificate below bachelor's level
 - ___ Bachelor's degree
 - ___ University certificate or diploma above bachelor's degree

10. Can you estimate in which of the following groups your household income falls? 

ADULT

Was the total household income ...

- Less than \$20, 000?
 - Less than \$10, 000?
 - Less than \$5, 000?
 - \$5, 000 or more?
 - \$10, 000 or more?
 - Less than \$15, 000?
 - \$15, 000 or more?
- \$20, 000 or more?
 - Less than \$40, 000?
 - Less than \$30, 000?
 - \$30, 000 or more?
 - \$40, 000 or more?
 - Less than \$50, 000?
 - \$50, 000 to less than \$60, 000?
 - \$60, 000 to less than \$80,000?
 - \$80, 000 or more?
- No Income

Residential Information

11. Please fill in the following table for your current and all past residences in Port Colborne.

Address ¹	Period of Stay ²		Type of Dwelling ³	Age of Residence ⁴
	From	To		

¹Please indicate street address, city, province, country, and postal code.

²Please indicate from MM/YYYY to MM/YYYY.

³Please indicate one of the following:

- Single Detached House
- Semi-Detached or Double (side-by-side)
- Garden House, Town-House or Row House
- Duplex (one above the other)
- Low-rise apartment (less than 5 stories)
- High-rise apartment (5 or more stories)
- Institution
- Collective dwelling (such as a Hotel/Motel, Rooming or Boarding House)
- Mobile home
- Farm or Acreage
- Other (please specify _____)

⁴Please indicate number of years.

12. If you have resided or are residing in more than one home concurrently, please fill in the following table: CHILD

Address	Percentage of Time Spent
#1	
#2	

Occupational Information

13. a) Do you now or have you ever worked in one of the following industries/occupations: Y/N ADULT.

b) If yes, please specify which industry/occupation:

- | | |
|--------------------------------|-----------------------------------|
| 1 - Underground mining | 8 - Welding |
| 2 - Smelting | 9 - Brazing |
| 3 - Metal Refining | 10 - Sintering |
| 4 - Foundry work | 11 - Plumbing |
| 5 - Steelmaking | 12 - Metal plating/electroplating |
| 6 - Metal Cutting and grinding | 13 - Shipbuilding/breaking |
| 7 - Boiler maker/repairer | 14 - Lumberyard/Sawmill |

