14. If yes to question 13. a), please provide details of any employment that falls into one of the categories listed above.

	Job Description (employer, city, job title)	Job Activity	Duration of Employment (years, months)
1			
2			

Lifestyle/Dietary Information

15. What is your primary source of drinking water?

- Municipal water
- Well water
- Bottled water

16. a) Do you have a garden, or participate in a community garden? Y/N ADULT

- b) If yes, do you grow:
- flowers
 - fruits
 - vegetables

17. How frequently do you engage in each of the following non-occupational hobbies or activities? ADULT SPECIFIC

- | | |
|--------------------|---------------------------------|
| a) painting* | Never, Rarely, Sometimes, Often |
| b) landscaping | Never, Rarely, Sometimes, Often |
| c) renovations | Never, Rarely, Sometimes, Often |
| d) automotive work | Never, Rarely, Sometimes, Often |

* We are interested in paints that are known to contain metals, such as, older water-based paints (pre-1992 paint may contain mercury), older lead based paint, or hobby/artist paints (may contain metals).

18. Does anyone in this household smoke regularly inside the house? 

- Yes
- No

19. At the present time do you smoke cigarettes daily, occasionally or not at all? 

- Daily (Go to Q20)
- Occasionally (Go to Q22)
- Not at all (Go to Q24)
- DK, R (Go to Q30)

20. At what age did you begin to smoke cigarettes daily? 

__ Age (MIN: 5) (MAX: current age) (Go to Q22)

21. How many cigarettes do you smoke each day now? 

__ Number of cigarettes (MIN: 1) (MAX: 99) (Go to Q30)

22. On the days that you do smoke, about how many cigarettes do you usually have? 

__ Number of Cigarettes (MIN: 1) (MAX: 99) (Go to Q23)

23. In the past month, on how many days have you smoked 1 or more cigarettes? 

__ Number of Days (MIN: 0) (MAX: 30) (Go to Q24)

24. Have you ever smoked cigarettes daily? 

- Yes (Go to Q25)
- No (Go to Q28)
- DK, R (Go to Q28)

25. At what age did you begin to smoke (cigarettes) daily? 

__ Age (MIN: 5) (MAX: current age) (Go to Q26)

26. How many cigarettes did you usually smoke each day? 

__ Number of Cigarettes (MIN: 1) (MAX: 99) (Go to Q27)

27. When did you stop smoking daily? Was it: 
- ... Less than one year ago? (Go to Q28)
 - ... 1 to 2 years ago? (Go to Q28)
 - ... 3 to 5 years ago? (Go to Q28)
 - ... More than 5 years ago? (Go to Q28)
 - DK, R (Go to Q28)

If Q19 = (current daily or occasional smoker) or if Q19 = DK or R, go to Q30.

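### Questions 13 and 14 record metal work as now-or-ever with a duration but no dates, so current and past occupational exposure cannot be separated

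*Protocol*

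**What the plan says.** In Appendix 10.1, question 13a is a single adult-only item: "Do you now or have you ever worked in one of the following industries/occupations: Y/N ADULT". Question 13b asks which industry. Question 14 asks for employer, city, job title and job activity, and its only timing column is "Duration of Employment (years, months". Section 6.2.1.2 describes the same content: "Details are collected for job description, activity, and duration of employment". Mock Table 4 in section 6.5.1 reports the row "Occupation related to Exposure" as Yes or No.

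Section 3.2.1.1.2 defines exposure as total exposure, including residential and occupational sources, and says that "detailed questions are included that encompass these areas to gauge both current and past individual exposure".

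On the metal tests, section 3.4 says both "The level of CoCs detected in the body measure the level of metal at that moment of time" and "The measures will not be able to differentiate between recent exposure or levels of metal from a previous or historical exposure".

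Section 6.4 plans to "examine the concordance between the exposure measures from the laboratory and the summary measure estimated from the questionnaire", and codes questionnaire exposure in two groups for the odds ratios. The footnotes to Tables 9 and 12, which compare metals between Area 3 and the other areas, adjust for age and sex only.

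**The concern.** A urine metal level is a measurement at one time, and the assay cannot show whether the exposure behind it was recent. Only the questionnaire could supply that timing. For occupation it does not: a welder at work this week and someone who left a foundry decades ago both answer Yes to question 13a and fall in the same row of Table 4.

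Two uses of the data are affected. First, if only some of the ever-employed are still exposed at work, a now-or-ever indicator dilutes the agreement between questionnaire and laboratory exposure. Second, if current metal employment differs between Area 3 and the rest of the city, the urine-metal comparison mixes workplace with residential exposure. An adjustment for ever having done such work would not remove this.

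The gap lies in data capture, so no later analysis plan can close it. Section 4.5 says that the link between identifier and identity is erased once the data are validated, so participants could not be asked again after that.

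**Working it through.** **Is the timing collected anywhere else?** The relevant items of Appendix 10.1, side by side:

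| Exposure | Item | Timing recorded |
|---|---|---|
| Residence | Q11 | From/To, month and year |
| School | Q36 | Year to year |
| Smoking | Q19, Q24 | Present smoking asked separately from ever daily smoking |
| Metal work | Q13, Q14 | Now-or-ever, plus length in years and months |

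No other item gives employment status or job dates. Age and job length do not fix them either: a job of five years in a person of 50 may have ended decades ago or may continue.

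**Effect on the concordance.** The documents give no figure to reproduce. Suppose that a share c of the ever-employed are current workers, and that only current work raises (log) urine metal, by D. The ever-versus-never difference is then c × D:
- c = 10%: 0.10D
- c = 25%: 0.25D
- c = 50%: 0.50D

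The data as collected identify neither c nor D. This dilution applies if the questionnaire summary in section 6.4 includes occupation; that section does not define the summary.

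**Effect on the area comparison of urine nickel.** Only the group size of 500 v 500 comes from the Protocol (section 6.1.1). The rest is assumed:
- log-SD of urine nickel: 0.7
- ever employed in a listed trade: 30% in both areas
- ratio of urine nickel with current work: 2
- still in such work among the ever-employed: 20% in Area 3 and 45% elsewhere, a gap of 0.25
- no true area effect

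Bias on the log scale after adjusting for ever = ln(ratio) × P(ever) × gap = 0.693 × 0.30 × 0.25 = 0.052. Since exp(0.052) = 1.053, this is about 5%.

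SE = 0.7 × √(2/500) = 0.0443, so z = 0.052 / 0.0443 = 1.17. A two-sided 5% test then rejects with probability P(Z > 1.96 − 1.17) + P(Z < −1.96 − 1.17) = 21.7%.

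Simulation by linear regression agrees: 21.5% when adjusted for ever, and 5.4% when adjusted for current work (4,000 runs each). With no occupational adjustment the bias is the same, because P(ever) is equal in both areas: 0.693 × (0.30 × 0.45 − 0.30 × 0.20) = 0.693 × 0.075 = 0.052. Simulated rejection was 21.4%.

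**Sensitivity to the assumptions** (same formula):

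| Ratio | P(ever) | Gap | Rejection |
|---|---|---|---|
| any | any | 0 | 5% |
| 1.5 | 30% | 15 points | 7.0% |
| 2 | 30% | 10 points | 7.6% |
| 2 | 15% | 25 points | 9% |
| 2 | 30% | 25 points | 21.7% |
| 3 | 30% | 30 points | 60.8% (56.3% simulated) |

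**The case against.** The strongest reply is that the form does what the Protocol says it does. Section 3.2.1.1.2 describes the exposure questions as covering where people lived and worked, for how long, and the nature of the job. Question 14 asks this. The phrase on current and past exposure describes the whole question set and does not promise a split for each job. That stands: a reader might infer a flat contradiction, but the documents support only that a stated aim is poorly served.

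A reader might also infer from section 3.4 that the current job is the only occupational confounder of a urine level. Section 3.4 does not say so. It also states that the assay cannot separate recent from historical exposure, which leaves room for past work to contribute. That sentence makes timing from the questionnaire more useful, not less. The section's general mention of limited exposure data does not cover the missing job dates.

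Third, the plan specifies no adjustment for ever having done metal work. Tables 9 and 12 adjust for age and sex, and occupation is absent from the headed confounder groups in section 3.3 and from the examples in section 6.4. The rejection rates are therefore illustrations, not properties of an analysis that the Protocol commits to. This stands, but section 3.3 admits a priori confounders and the list in section 6.4 is open. Under the illustrative inputs, the comparison without occupational adjustment carries the same bias.

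Fourth, the documents give no reason to expect an area gap in current metal employment, nor its direction. This stands too, and it is why the size remains open.

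Finally, a reader might add that current workers are healthier than leavers, so that metal-disease odds ratios are pulled down. Nothing in the documents supports or quantifies this, and it forms no part of the point.

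**Conclusion.** The point holds as a gap in data capture that is cheap to close. Present and past metal work cannot be separated from what questions 13 and 14 collect, although the same form records timing for residence, school and smoking. The consequence is a weaker laboratory-questionnaire concordance, where occupation enters the summary, and no means of adjusting urine-metal comparisons for current work.

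The size is conditional. It is nil if current metal employment does not differ by area. It is about 5% in urine nickel, with about 22% false rejection, under the central assumptions, and 7% to about 60% across the non-zero gaps examined. None of these inputs except the group size comes from the Protocol, so the figures show what could happen and not what is expected. Nor do the two workers in the example have identical records: employer, title, activity, duration and date of birth are kept. What these fields cannot establish is whether the job is current.

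**What to change.** 1. In question 14, replace the duration column with From/To (MM/YYYY, with 'present' allowed), as in question 11. Duration can still be derived.
2. In mock Table 4, split the occupation row into Current, Past only and Never.
3. In section 3.3, name current metal work as an a priori candidate confounder, subject to that section's own 10% change rule. Apply it to the urine-metal comparisons (Tables 9 and 12, now adjusted for age and sex only) and to the urine-metal odds ratios. Dates alone would not change those analyses.

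The cost is one column heading, one recode, slightly more interview time and some recall error in dates. Questions 13 and 14 carry no source mark, and the rule in section 4.2.2.1 against rewording covers only borrowed items, so no external comparison should be lost. The same section places a pre-test before fielding, where the new column can be tried.

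### Printed skip codes leave Q21 (current cigarettes per day) unreachable, take daily smokers to a quit-time question, and never ask Parkinson's cases their age at diagnosis

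*Protocol*

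**What the plan says.** All item numbers are from Protocol, Appendix 10.1. The Current Medical Health Status section restarts its numbering, so the smoking items and the Parkinson's items belong to different series.

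**Smoking (Lifestyle/Dietary Information).**
- Q19, current smoking: "Daily (Go to Q20" and "Occasionally (Go to Q22".
- Q20, age at starting daily smoking: "Age (MIN: 5) (MAX: current age) (Go to Q22".
- Q21: "How many cigarettes do you smoke each day now", with the exit "Number of cigarettes (MIN: 1) (MAX: 99) (Go to Q30".
- Q22, usual number on smoking days: "Number of Cigarettes (MIN: 1) (MAX: 99) (Go to Q23". Q23 then goes to Q24.
- Q24, ever smoked daily: Yes leads to Q25 (starting age), Q26 (past amount) and Q27, "When did you stop smoking daily? Was it". Q27 offers four intervals since stopping, plus don't know/refused.
- After Q27, a filter sends current daily and occasional smokers to Q30.

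**Parkinson's disease (Neurological).** At Q42, Yes and No both carry a skip to Q44, and Don't Know/Refused carries none. Q43 asks age at first diagnosis.

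Section 4.2.2.1 says the smoking questions come from the Canadian Community Health Survey (CCHS). Section 6.2.1.4 says the medical section records how long a disease has been present as well as whether it is present.

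**The concern.** The printed routes contradict the instrument's own structure. Q21 has an exit but no entry. Q22 is where occasional smokers enter, yet daily smokers are sent there too. Q27 presupposes that daily smoking has ended, and the filter that recognises current smokers comes only after it. At Q42, a person with the disease skips the follow-up and a person who does not know or declines to answer receives it.

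Three things are at stake: the current-consumption item borrowed from the CCHS, clean answers to the former-smoker items, and disease duration for one listed condition. Section 5.1 has questionnaires completed on paper case report forms, and section 5.3 has them double-entered. The protocol describes no electronic skip logic that would override a printed code, and double entry would faithfully reproduce a misrouted answer.

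**Working it through.** The plan gives no figure to reproduce here, so the check is a trace of every route. The inputs are the printed skip codes for Q19 to Q30 and Q42 to Q44. One assumption is made: the filter after Q27 is applied to anyone about to enter Q28, including those sent there from Q24.

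**Smoking, as printed**

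| Q19 answer | Distinct paths | Route |
|---|---|---|
| Daily | 3 | 20, 22, 23, 24; then 25, 26, 27, 30 if Yes at Q24, or 30 if No or don't know/refused |
| Occasionally | 3 | 22, 23, 24; then as above |
| Not at all | 9 | 24, with or without 25 to 27, then 28, with or without 29, to 30 |
| Don't know/refused | 1 | 30 |

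Total: 3 + 3 + 9 + 1 = 16 paths, and none contains Q21. A daily smoker answering truthfully says Yes at Q24 and so reaches Q27.

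**Smoking, with Q20 sent to Q21.** The only daily-smoker path is 19, 20, 21, 30. The other routes do not change, giving 1 + 3 + 9 + 1 = 14 paths. That this closes cleanly, using the exit already printed at Q21, is the evidence that it was the intended branch. The CCHS routing itself is not in the documents and is not relied on.

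**What a daily smoker is asked beyond Q20, as printed**

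| Item | Status |
|---|---|
| Q22 | Answerable; for someone who smokes every day, close to cigarettes per day |
| Q23 | Answerable but uninformative |
| Q24 | Answerable |
| Q25 | Repeats Q20 |
| Q26 | Past tense, but answerable |
| Q27 | No valid option for a current daily smoker |

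**Parkinson's disease.** As printed, Yes goes to Q44, No goes to Q44, and Don't Know/Refused goes to Q43. At the comparable items (Q6 chronic bronchitis, Q8 emphysema/COPD, Q40 peripheral neuropathy), No and Don't Know/Refused skip the age question and Yes proceeds to it. Q42 departs from that pattern for two of its three answers.

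**The case against.** The strongest reply is that little the plan uses is lost, and most of it stands.

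- Status, starting age and an approximate amount are still collected for daily smokers, from Q19, Q20 and Q22.
- Mock Table 4 classes smoking as never, current, former or unknown, and Q19 = Daily settles that whatever Q27 says.
- Mock Tables 5 and 6 need only Parkinson's prevalence, which Q42 gives.
- Section 6.4 specifies no analysis of time since quitting, smoking duration or age at diagnosis. Mock Table 6, the external comparison, has no smoking row.
- Recent smoking is also measured by plasma cotinine and breath carbon monoxide (sections 3.2.2.5 and 3.3.6).

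A reader might infer more than the text supports, in three ways.

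- *About 300 misrouted interviews.* This comes from 30% × 1,000, but the 30% in section 6.1 is a hypothetical overall smoking rate used to explain sampling variation, not an estimate of daily smoking. Section 4.2.2 also describes the smoking-status questions as adult-specific. The documents give no usable count.
- *Six inapplicable questions per daily smoker.* The table above shows one truly inapplicable item, Q27, with some redundancy around it.
- *Contaminated former-smoker variables.* Every affected record carries Q19 = Daily, so Q25 to Q27 can be set aside with one condition.

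The pre-test in section 4.2.2.1 and the site coordinator's check in section 4.2.2.2.2 may well catch the errors, and section 4.3.1.1 calls this protocol a draft. That makes fielding the errors less likely but does not correct the printed codes. The trace also cannot exclude a label displaced at Q42 when the text was read, although neighbouring items came through in the expected pattern.

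**Conclusion.** Both routing errors are in the current text. Fielded as printed, Q21 would have no responses, daily smokers who answer Yes at Q24 would be asked when they stopped, and no Parkinson's case would give an age at diagnosis.

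The loss is small: Q21 as a separate item, some redundant or spurious answers to Q25 to Q27 that can be filtered out, and Q43 for what should be few people. The sample size, the mock-table rows and the smoking adjustment in the logistic models are not undermined, because status and approximate amount remain available.

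The conclusion assumes that interviewers follow the printed codes and that the filter after Q27 applies to everyone about to enter Q28. It is a correction to make before fielding, because Q21 and Q43 could be recovered later only by recontact, and section 4.5 plans to erase the link to identity once the data are validated.

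**What to change.** Change three routing codes in Appendix 10.1:

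1. Q20: exit to Q21 instead of Q22.
2. Q42, Yes: proceed to Q43.
3. Q42, Don't Know/Refused: go to Q44. No already does.

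Include one current daily smoker and one Parkinson's case among the scripted pre-test interviews, so that both branches are walked through. The cost before fielding is a reprint of the affected pages. If any interviews have already used the printed version, set Q25 to Q27 to not applicable where Q19 = Daily, use Q22 as the current amount and label it as such, and report Q21 and Q43 as not collected for those interviews.
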